2.0 Study objectives

The primary objective of the study is to compare CIN2+ cure rates at twelve-months post-treatment with the LMIC-adapted CryoPen[®], the WISAP thermoablator, and CO₂-based cryotherapy.

Secondary objectives of the study are:

- To measure patient acceptability of the CryoPen® and thermoablator with pain scores and surveys
- To actively assess side effects of cryotherapy and thermoablation including infection, pain, bleeding, discharge, and stenosis at a six-week post-treatment visit
- To evaluate the sensitivity of high-risk HPV DNA testing post-ablation

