Women will then undergo treatment with the LMIC-adapted CryoPen[®], the WISAP thermoablator, or CO₂-based cryotherapy. Patient pain will be evaluated four times during the treatment visit as described in section 5.2 below.

Images of the cervix will be taken with the EVA System Mobile ODT device before and after treatment. De-identified cervical images from the initial visit and the follow-ups will be made available to Mobile ODT. The company will use these images to help develop an Automated Evaluated System (AVE), a software algorithm to detect pre-cancerous lesions through images rather than laboratory tests. This algorithm is currently in development and the more images it "learns", the more accurate results it can obtain. If successful, AVE can greatly ease diagnosis and triage in low-income settings.

Six-week follow-up

Six weeks post-treatment, women will return for a visit to evaluate side-effects. Data will be collected on women who attend this visit at any time between 4 to 12 weeks post-treatment. If a woman does not attend this visit, she will still remain in the study and be invited to return at 12 months post-treatment. At the 6-week visit, women will complete a questionnaire to assess the presence of pain or cramps, bleeding, watery discharge, and malodorous discharge. Women will also be asked some questions about their attitudes and perceived acceptability of the treatment they received. Finally, women will be asked to answer a checklist to assess their compliance with post-treatment recommendations. In addition, a pelvic exam will be performed and vaginal samples will be collected and analyzed for bacterial vaginosis, yeast, gonorrhea, trichomonas, and chlamydia. If an infection is suspected, the provider may prescribe medication as necessary. The provider will note whether a vaginal culture swab can be introduced into the endocervix. If it cannot, stenosis will be diagnosed. Women will also be evaluated for acute clinical cervicitis at the follow-up visit and this will be recorded. Another photo will be taken with the Mobile ODT device.

12-month follow-up

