One year post-treatment, women will return for a follow-up visit to determine residual disease, which is the primary endpoint. Residual disease will be determined by colposcopy and four-quadrant biopsies. In addition, VIA, cytology, and high-risk HPV DNA testing with careHPV will be performed. Genotyping and next-generation sequencing will be repeated to differentiate between persistent and new infections. The goal is to evaluate which test has the highest sensitivity after an ablative treatment: VIA, cytology, or HPV.

We will use local health systems, including healthcare promoters, to encourage women to return for the follow-up visit. Attempts to contact women who do not return for this visit will continue until 18 months post-treatment. If a woman does not return within this time period, she will be considered lost to follow-up.

At the 12-month visit, the following procedures will be performed:

- 1. Pelvic examination
- 2. Urine pregnancy test
- 3. Unaided VIA
- 4. Cytology
- 5. High-risk HPV testing with careHPV
- 6. Colposcopic evaluation and impression
- 7. Four-quadrant microbiopsy protocol using the protocol for sensitive detection of any recurrent/untreated CIN2+.¹¹ All visible lesions in each quadrant of the cervix (12-3, 3-6, 6-9, and 9-12 o'clock) will be biopsied. Endocervical curettage (ECC) will be performed on all patients. If no lesion is visible in a given quadrant, the most suspicious appearing area in that quadrant will be biopsied.
- 8. Cervical swab collection for HPV genotyping using next-generation sequencing (NGS)

Treatment acceptability questions will again be administered at the end of this visit. Women diagnosed with recurrent/untreated CIN2+ on biopsy will be asked to return to undergo LEEP. Women with suspected cancer on biopsy will be referred to the local cancer hospital for standard of care.

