Statistical Power and Sample Size. With a total of 922 women with a diagnosis of CIN2+, 307 per treatment arm, the study will have at least 80% power (alpha = 0.05) to detect a non-inferiority margin difference of 10% between the cure fraction of CO₂-based cryotherapy (reference) and of the LMIC-adapted CryoPen® (experimental) and the WISAP thermoablator (experimental), for a range of efficacy (50% to 80%) for the reference treatment and 40% efficacy under the null hypothesis of inferiority. We chose a range of 50-80% efficacy for cryotherapy because although the literature suggests CO₂-based cryotherapy is 80% effective, the disease ascertainment by colposcopy following treatment in previous studies was before the recognition that colposcopy is not perfectly sensitive. Therefore, the disease ascertainment in those studies was not as rigorous as proposed in this study. To ensure that the study is sufficiently powered for a wide range of efficacies, we are selecting 50% efficacy for the control arm as the worst-case scenario for study power. In order to achieve a sample size of 922 with complete follow-up, we will enroll 1281 women with CIN2+ under the assumption that 10% will have contraindications for cryotherapy and 20% will be lost to follow-up at twelve months post-treatment.

Test of cure

Analytic Approach. Since all women returning for the twelve-month visit will undergo four-quadrant biopsies and LEEP if diagnosed with CIN2+, regardless of the baseline characteristics or ablative treatment, we can assess the test of cure performance (sensitivity, specificity, positive predictive values (PPV), and negative predictive values (NPV)) of each test (VIA, cytology, and high-risk HPV DNA) for recurrent CIN2+ and CIN3 diagnosed by local and expert pathology. Performance will be stratified by quartiles of age and by the baseline diagnosis. McNemar chi-square will be used to test whether differences in sensitivity and specificity are significant (p < 0.05). A method developed by Leisenring *et al.* ¹² will be used to test for significant differences in PPV and NPV.

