5.2 Study procedures for cervical ablations

For the traditional cryotherapy arm, providers will use a MedGyn cryotherapy unit with a 19 or 25 mm conical tip supplied with a refillable tank of medical grade CO₂. For the experimental CryoPen[®] arm, providers will use LMIC-adapted CryoPen[®] prototype with a 19 mm conical tip. For the thermoablator arm, providers will use a handheld WISAP thermoablator (model C3) with a 20 mm conical tip.

Anesthesia is not required for cervical ablation procedures and none will be provided routinely in this research study. Analgesics may be prescribed for discomfort after the procedure. Study coordinators will verbally ask study participants to assess their pain

using the Wong Baker Faces Scale (Figure 2),¹³ a well-validated and widely used self-assessment tool. This scale was originally developed for use with children but is now available in many languages, including Spanish and Mandarin Chinese, and is used to improve communication between patients and providers. It utilizes five simple drawings of faces depicting different levels of pain, each shown above a number from 0 (no pain) to 10 (worst possible pain). Patients can use the expressions on the faces to rate their own experience according to the corresponding number. Pain will be assessed at 4 points: before speculum insertion (baseline), after speculum insertion but before treatment, during treatment, and after speculum removal.

Wong-Baker FACES™ Pain Rating Scale

Figure 2. FACES and numeric pain rating scale

Cervical photographs will be taken immediately pre- and post-procedure for participants who have consented to photographs. Photographs will provide additional documentation of the cervix anatomy to corroborate the clinical evaluation whether the anatomy of the cervix could have interfered with a good contact by the treatment probe at cervix positions 3, 6, 9 or 12 (as on a clock face).

Each study procedure is estimated to take approximately 10-15 minutes. The remainder of the time will be spent preparing the participant and taking cervical photographs. The six-week and 12-month follow-up visits (described in section 3.1) are expected to take about 15 minutes. All women will undergo liquid-based cytology, VIA, and HPV testing. Women suspected of having invasive cancer at the follow-up visit will be referred for appropriate management.

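### Asking the 12-month acceptability questions at the end of the visit, after at least four biopsies and an endocervical curettage, risks carry-over of procedure discomfort into that survey

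*Combined protocol and SAP*

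**What the plan says.** Section 2.0 (Study objectives) lists this secondary objective: "To measure patient acceptability of the CryoPen® and thermoablator with pain scores and surveys". The documents give it three sources of data.

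- **Treatment day, pain scores (section 5.2).** "Pain will be assessed at 4 points: before speculum insertion (baseline), after speculum insertion but before treatment, during treatment, and after speculum removal".
- **Six weeks, survey (section 3.1, Six-week follow-up).** "Women will also be asked some questions about their attitudes and perceived acceptability of the treatment they received".
- **12 months, survey (section 3.1, 12-month follow-up).** "Treatment acceptability questions will again be administered at the end of this visit".

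The 12-month visit has eight listed procedures, among them a pelvic examination, VIA, cytology, HPV sampling and colposcopy. On biopsies, section 3.1 says: "If no lesion is visible in a given quadrant, the most suspicious appearing area in that quadrant will be biopsied". It adds: "Endocervical curettage (ECC) will be performed on all patients". Section 5.2 gives the length of the visit: "The six-week and 12-month follow-up visits (described in section 3.1) are expected to take about 15 minutes".

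The documents do not give the wording or scale of the acceptability items. They name no main time point for acceptability and contain no analysis plan for it.

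**The concern.** A woman's opinion of an ablation done a year earlier is collected minutes after a different and invasive set of procedures. If the discomfort of the day colours her answer, the survey partly measures the biopsies and the ECC. The stated objective is to measure acceptability of the CryoPen and the thermoablator, so a shift in the absolute level is an error in the quantity of interest, even when all arms shift alike. Noise unrelated to the device would also make device comparisons less precise.

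The six-week survey does not fully cover the gap. Section 3.1 treats the six-week visit as not essential, and a woman who misses it stays in the study and is invited back at 12 months. For her, the end-of-visit survey at 12 months is the only acceptability survey.

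**Working it through.** The plan has no figure for acceptability to reproduce. The check sets the visits side by side and then illustrates the direction of an effect.

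**1. Which measurements follow biopsy or ECC**

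| Measurement | Place | Biopsy or ECC beforehand at that visit? |
|---|---|---|
| Four pain ratings | 5.2, treatment day | None listed |
| Six-week survey | 3.1, Six-week follow-up | None listed |
| 12-month survey | 3.1, 12-month follow-up | Yes: at least 4 biopsies (4 quadrants × at least 1) plus ECC, in all women |

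Only the third row is exposed. The six-week text mentions the questions before the pelvic examination but does not fix an order.

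**2. Whether the burden differs by arm**

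Section 3.2 confirms that the biopsies apply to everyone who returns: "Since all women returning for the twelve-month visit will undergo four-quadrant biopsies", whatever the ablative treatment. The required minimum is therefore equal across arms. One qualification is an inference: all visible lesions are biopsied, so a woman with several may have more than four biopsies. If residual disease differed by device, the biopsy burden could differ somewhat too.

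**3. Illustration of direction**

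Inputs: 307 women per arm (section 3.2; 922 / 3 ≈ 307). Assumed, not in the documents: true acceptability of 90% and 80% in two arms, and a share *m* of favourable answers lost equally in both because of the day's procedures. The test is two-sided at 5% with a normal approximation.

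Formulas: observed proportion = p(1 − m); observed difference = (pA − pB)(1 − m); SE = √{[qA(1 − qA) + qB(1 − qB)] / 307}, where q is the observed proportion; expected z = difference / SE; power ≈ Φ(z − 1.96).

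- m = 0: SE = √[(0.09 + 0.16)/307] = 0.0285; z = 0.10/0.0285 ≈ 3.5.
- m = 10%: 0.90 × 0.90 = 0.81 and 0.80 × 0.90 = 0.72; SE = √[(0.1539 + 0.2016)/307] = 0.0340; z = 0.09/0.0340 ≈ 2.6.

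| m | Observed proportions | Difference (points) | Power |
|---|---|---|---|
| 0 | 90.0% vs 80.0% | 10.0 | 94% |
| 5% | 85.5% vs 76.0% | 9.5 | 85% |
| 10% | 81.0% vs 72.0% | 9.0 | 75% |
| 30% | 63.0% vs 56.0% | 7.0 | 43% |

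Under this mechanism an equal loss lowers the level and shrinks a difference. It does not create a difference or reverse its sign.

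The result depends on the assumed mechanism. If both arms instead lost 10 percentage points (80% vs 70%), the difference would stay at 10 points, and z = 0.10/√[(0.16 + 0.21)/307] = 0.10/0.0347 ≈ 2.9. Only precision would suffer.

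**The case against.** The strongest reply is that carry-over is not shown. The item wording is not in the documents, and both passages describe the questions as being about the treatment, so women may well keep the ablation apart from the day's procedures. This stands: the point is a risk in the design, not a demonstrated bias.

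A reader might infer more, and the documents do not support it:

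- *That the whole acceptability outcome is contaminated.* The pain scores come from the treatment day, and no biopsy or ECC is listed at six weeks. The 12-month survey is a repeat.
- *That one device is favoured, or that true differences are hidden.* The required procedures are the same in all arms. In the 10% illustration a 10-point difference becomes 9 points with an expected z of about 2.6, which is weaker but not hidden.
- *That a fall from six weeks to 12 months would be read as declining satisfaction.* No such comparison is planned.
- *That the six-week questions are known to precede the examination.* That order is only suggested by the order of the paragraph.

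It is also true that the primary endpoint, the non-inferiority decision, the safety assessments and the interim rule do not use these answers. What remains is that the plan fixes the less favourable order without giving a reason, when a neutral order is available.

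**Conclusion.** The point holds as a minor one. The 12-month acceptability survey is placed where procedure discomfort could carry over into it, for every woman who returns (about 922 planned). The likely consequence is a lower absolute rating at 12 months and some loss of precision between devices. The pain scores and the six-week survey are not exposed to biopsy or ECC.

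The size cannot be derived from the documents. The illustrative fall in power from 94% to between 85% and 43%, for m between 5% and 30%, rests on assumed acceptability rates, an assumed proportional loss equal in all arms, and 307 respondents per arm. It shows direction only. The point matters most for women who miss the six-week visit.

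**What to change.** In section 3.1, 12-month follow-up, state that the treatment acceptability questions are asked at the start of the visit, before the pelvic examination and any sampling. In the six-week section, state the same order, so that the two surveys are taken under comparable conditions.

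The cost is a sentence in each place and a reordered visit form. It needs no extra procedure, staff or visit time, and it leaves the primary endpoint and clinical care unchanged.

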3.2 Sample size and statistical analyses

Treatment efficacy

Analytic Approach. The primary analysis will follow an "intent to treat" approach, and we will conduct an additional sub-analysis excluding patients referred to excisional treatments after randomization. Similarity of the two study arms in terms of follow-up rates, distribution of individual and demographic variables, and disease distributions will be assessed. We will calculate the cure fraction and the corresponding binomial 95% confidence interval (95% CI) of each treatment as the percentage of women diagnosed with CIN2+ at the twelve-month visit. The non-inferiority of the LMIC-adapted CryoPen[®] and the WISAP thermoablator relative to CO₂-based cryotherapy will be assessed by calculating 95% CIs for the differences (LMIC-adapted CryoPen® minus CO₂-based cryotherapy and WISAP thermoablator minus CO₂-based cryotherapy) in cure fractions. Non-inferiority will be concluded if the lower confidence bound is greater than the non-inferiority margin (-10%). Exploratory analysis of the effectiveness and differences between arms will be evaluated within strata defined by quartiles of age and by the baseline diagnosis. Both the local and expert pathologists' diagnoses will be used in these analyses. As warranted, a logistic regression model will be used to mutually control for all important variables and chance differences between study arms to identify the key determinants of treatment failure and differences (if any) in effectiveness between treatments.

Statistical Power and Sample Size. With a total of 922 women with a diagnosis of CIN2+, 307 per treatment arm, the study will have at least 80% power (alpha = 0.05) to detect a non-inferiority margin difference of 10% between the cure fraction of CO₂-based cryotherapy (reference) and of the LMIC-adapted CryoPen® (experimental) and the WISAP thermoablator (experimental), for a range of efficacy (50% to 80%) for the reference treatment and 40% efficacy under the null hypothesis of inferiority. We chose a range of 50-80% efficacy for cryotherapy because although the literature suggests CO₂-based cryotherapy is 80% effective, the disease ascertainment by colposcopy following treatment in previous studies was before the recognition that colposcopy is not perfectly sensitive. Therefore, the disease ascertainment in those studies was not as rigorous as proposed in this study. To ensure that the study is sufficiently powered for a wide range of efficacies, we are selecting 50% efficacy for the control arm as the worst-case scenario for study power. In order to achieve a sample size of 922 with complete follow-up, we will enroll 1281 women with CIN2+ under the assumption that 10% will have contraindications for cryotherapy and 20% will be lost to follow-up at twelve months post-treatment.

Test of cure

Analytic Approach. Since all women returning for the twelve-month visit will undergo four-quadrant biopsies and LEEP if diagnosed with CIN2+, regardless of the baseline characteristics or ablative treatment, we can assess the test of cure performance (sensitivity, specificity, positive predictive values (PPV), and negative predictive values (NPV)) of each test (VIA, cytology, and high-risk HPV DNA) for recurrent CIN2+ and CIN3 diagnosed by local and expert pathology. Performance will be stratified by quartiles of age and by the baseline diagnosis. McNemar chi-square will be used to test whether differences in sensitivity and specificity are significant (p < 0.05). A method developed by Leisenring *et al.* ¹² will be used to test for significant differences in PPV and NPV.

Statistical Power. The statistical power for comparing sensitivity for the test of cure for VIA, cytology, and high-risk HPV testing is dependent on sample size of the efficacy study and the actual efficacy. We are enrolling 1281 women to assure that we have 930 women with a twelve-month follow-up. The larger the number of women who return for their follow-up, the larger the sample size for a given level of efficacy will be. The more efficacious the treatments, the smaller the sample size will be. Assuming 70% efficacy in treatment (30% recurrence), results of tests for cure will be available for 279 women with recurrence. This will provide 85% power (0.05 two-sided alpha) to detect a 10% difference in sensitivity between tests assuming 20% discordance between tests.

Interim Analysis of Cure Fractions. An interim analysis of cure fractions will be performed after approximately 2 years of study opening, when approximately 1/3 of the women have been enrolled. A confidence interval will be calculated for the difference (LMIC-adapted CryoPen® minus CO₂-based cryotherapy and WISAP thermoablator minus CO₂-based cryotherapy) in cure fractions. If the upper bound of the confidence interval is lower than the non-inferiority margin (-10%), then treatment modification or termination may be considered. The confidence interval will be calculated using an alpha calculated using an alpha time-squared spending function to maintain an overall 5% Type I error (one-sided).

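### The cure fraction is defined as the percentage of women with CIN2+ at 12 months, which reverses the non-inferiority decision if followed as written

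*Combined protocol and SAP*

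**What the plan says.** Section 3.2, Treatment efficacy, Analytic Approach, gives the primary estimate and the decision rule in consecutive sentences.

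- Definition: the cure fraction is calculated "of each treatment as the percentage of women diagnosed with CIN2+ at the twelve-month visit".
- Contrast: non-inferiority "will be assessed by calculating 95% CIs for the differences", taken as experimental minus reference for each device, for example "WISAP thermoablator minus CO₂-based cryotherapy) in cure fractions".
- Decision: "Non-inferiority will be concluded if the lower confidence bound is greater than the non-inferiority margin (-10"%).

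The interim analysis, described in 3.2 and again in 12.0, uses the same differences in cure fractions: "If the upper bound of the confidence interval is lower than the non-inferiority margin (-10"%), modification or termination of a treatment may be considered.

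No other section gives a formula for the cure fraction. Elsewhere cure and efficacy have their ordinary meaning. The primary objective (2.0) is to compare cure rates. The power text in 3.2 works "for a range of efficacy (50% to 80%) for the reference treatment and 40% efficacy under the null hypothesis of inferiority". The test-of-cure power text in 3.2 equates 70% efficacy with 30% recurrence. Section 9.0 cites cure rates of 77% to 93% after cryotherapy.

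**The concern.** The percentage of women with CIN2+ at 12 months measures failure, so a higher value is worse. A lower bound above -10% for device minus control shows non-inferiority only when a higher value is better. Combined with the definition as written, the rule asks whether the device reduces residual disease by no more than 10 points. A worse device meets that easily and a much better one does not.

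This is the operative definition of the quantity to which the margin applies. Other wording also makes a literal reading easy to program: 3.1 names residual disease as the primary endpoint, so an analyst could code CIN2+ as 1 and then apply the -10% lower-bound rule. If the direction is corrected only after data have been seen, the correction is a departure from the written primary definition and has to be defended as such.

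**Working it through.** **Inputs from section 3.2.** "With a total of 922 women with a diagnosis of CIN2+, 307 per treatment arm"; margin -10%; a 95% interval for the difference; reference efficacy 50% to 80%, with 40% as the inferior value. The plan names no interval method for the difference, so a Wald interval with z = 1.96 is assumed.

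**The plan's own sample size.** The plan states that "the study will have at least 80% power (alpha = 0.05) to detect a non-inferiority margin difference of 10"%. With 50% efficacy in both arms, margin 0.10, one-sided alpha 0.05 and 80% power:

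n = (1.645 + 0.842)² × (0.25 + 0.25) / 0.10² = 309.1, so 310 per arm.

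Using the variance at 50% against 40% for the null term gives 305. The stated 307 lies between these and is built on efficacy in the ordinary direction, so the definition error does not affect it.

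**The decision rule.** Let p_C and p_D be the true CIN2+ proportions on control and device, and n = 307 per arm.

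- Difference as written: d = p_D − p_C.
- Difference as intended: (1 − p_D) − (1 − p_C) = −d.
- SE = √[p_C(1 − p_C)/n + p_D(1 − p_D)/n], the same for both readings.
- Non-inferiority is declared if the estimated difference − 1.96 × SE > −0.10.

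Worked case, p_C = 0.30 and p_D = 0.40 (a true deficit exactly at the margin):

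- SE = √(0.21/307 + 0.24/307) = 0.0383.
- As written: expected difference +10.0%, interval +2.5% to +17.5%. The lower bound is well above -10%.
- As intended: expected difference -10.0%, interval -17.5% to -2.5%. The lower bound is below -10%.

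**Probability of declaring non-inferiority**, by exact summation over the two binomial distributions:

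| CIN2+ control | CIN2+ device | As written | As intended |
|---|---|---|---|
| 30% | 40% (at the margin) | 99.9% | 2.5% |
| 50% | 60% (the plan's null, 50% vs 40% efficacy) | 99.9% | 2.4% |
| 30% | 50% (clearly worse) | about 100% | below 0.001% |
| 30% | 15% (clearly better) | 0.03% | about 100% |
| 30% | 30% (equal) | 77.3% | 77.3% |

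The last row shows why a power calculation at equal efficacy cannot reveal the error: the two readings agree when the arms are equal.

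**Interim rule.** Read literally, an upper bound below -10% means the device has far less residual disease than control. For illustration, take one third of 307, about 102 per arm, as evaluable (an assumption; the plan refers to one third enrolled). Time-squared spending of a one-sided 5% then gives 0.05 × (1/3)² = 0.0056, z = 2.54. By normal approximation, the literal rule flags a better device as follows:

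- 10 points better (50% vs 60% cure): 0.6%.
- 15 points better: 3.5% (50% vs 65% cure), 4.7% (70% vs 85%), 7.6% (80% vs 95%).
- 30 points better (50% vs 80% cure): 73%, or 88% with an unadjusted 95% interval.

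A worse device is essentially never flagged.

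**The case against.** The strongest reply is that this is an evident slip. The quantity is called a cure fraction, the objective is cure rates, the power text and the recurrence example run in the correct direction, and both decision rules carry the sign for higher is better. An analyst would have to label residual disease as cure to obtain the reversed result. The endpoint itself (12-month biopsy, read by pathologist consensus) is not inverted; one clause describing a derived percentage is. It could also be argued that women diagnosed with CIN2+ was meant as the denominator, with the cured numerator left out, although the reference to the twelve-month visit makes that reading strained.

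Much of this stands. The intent can be recovered, the harm arises only if the sentence is implemented literally, and sample size and power are untouched. The interim consequence is small for moderate superiority, as the figures above show, and an interim flag is not binding. The reversal also depends on a real difference: with equal arms the two readings agree.

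None of it makes the definition correct. The other sections show that it is wrong, and none supplies a competing formula. A pre-specified primary definition has to give the right answer when followed.

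**Conclusion.** The concern holds. The only definition of the primary estimate in the plan is the failure proportion, and it contradicts the decision rule that follows it. Applied literally, a device at the plan's own inferior value passes 99.9% of the time against 2.4% as intended, and a device that halves residual disease from 30% to 15% passes 0.03% of the time against almost 100%. These figures assume 307 evaluable women per arm, a two-sided Wald 95% interval and the true rates shown. The direction of the error does not depend on those choices. It must be corrected before analysis, even though the cause is most likely a wording slip.

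**What to change.** In 3.2, define the cure fraction as the number of women with no CIN2+ or worse on the 12-month consensus pathology described in 5.3, divided by the number of women in the primary analysis set. State that this definition governs the final -10% rule and both statements of the interim rule (3.2 and 12.0).

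Specify the denominator in the same sentence. The plan calls for intention to treat and expects 20% loss to follow-up, so it must say how women without a 12-month result are handled. Do not define cure simply as one minus the CIN2+ fraction unless every woman in the set has a result. With all randomised women in the denominator, that form would count lost women as cured, while the direct form counts them as failures.

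An equivalent alternative, when every woman in the set has a result, is to keep the residual-disease proportion and reverse both rules: non-inferior if the upper bound is below +10%, and the interim rule triggered if the lower bound is above +10%.

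The cost is a short text amendment, with no change to data collection, sample size or procedures.
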